## Synopsis:

This study is prospective, randomized trial in which the efficacy of liposomal bupivacaine (Exparel®) is compared to standard bupivacaine local surgical site injection in reducing total IV and oral morphine equivalents required after laparoscopic bariatric surgery. Exparel® is a 72-hour bupivacaine that is FDA approved for surgical site infiltration and is slowly released from tissue over the course of three days. Having a long acting local anesthetic should provide better pain control than conventional bupivacaine which has a 3.5-hour half-life. Currently, standard surgical site infiltration in laparoscopic bariatric surgery includes bupivacaine but not Exparel®. In some studies, the use of liposomal bupivacaine has been shown to decrease pain and narcotic use after surgery. This has not yet been studied in bariatric patients and the use of liposomal bupivacaine can potentially improve patient post-operative pain control, decrease narcotic use, decrease hospital length of stay and readmission rates and improve patient satisfaction after bariatric surgery.

### **Hypothesis:**

Surgical site infiltration of liposomal bupivacaine compared to standard bupivacaine will reduce in hospital total oral and IV morphine equivalents required after laparoscopic bariatric surgery.

# **Background:**

Although recovery after laparoscopy is brief compared to open laparotomy, pain control from port site incisions can remain challenging. Postoperative pain often involves narcotics and can lead to side effects of nausea, altered gastrointestinal motility such constipation, and potential addiction. Brummett et al found around 6% rate of chronic opioid use after major and minor surgery despite being opioid naïve prior to surgery[1]. In bariatric patients, there is a paucity of literature regarding pain control. Budiansky et al. suggest for patients with morbid obesity that pain management cannot adhere to standard protocols which generally includes administration of opioids. Drugs are typically dosed to weight however the distribution of lean and adipose tissue of a patient with morbid obesity will change the clearance and effect of common medications. In addition, physiologic changes and other co-morbidities relating to obesity including obstructive sleep apnea can limit typical pain regimens or even augment the potential side effects [2]. Minimizing the use of narcotics in bariatric patients is beneficial even in those with chronic opioid use. Bariatric patients with chronic opioid use have an increased prevalence of opioid use several years after bariatric surgery[3]. Therefore, prevention of opioid use after surgery by optimizing intraoperative and postoperative pain control is beneficial.

Currently, standard local injections of bupivacaine at port sites are performed during laparoscopic bariatric surgery. New techniques such as intrathecal opioid administration, bupivacaine continuous catheter infusions or continuous intravenous infusion of dexmedetomidine have been described [4-6]. Recently, the beneficial use of liposomal bupivacaine in pain control has been described in laparoscopic and open colorectal, gynecological and orthopedic surgeries. Exparel® is a 72-hour slowly releasing bupivacaine that is FDA approved for surgical site infiltration. The use of

liposomal bupivacaine in local surgical site injection has been studied in non-bariatric surgeries in improving patient post-operative pain control and decreasing length of hospital stay and improving patient satisfaction [7-9]. However, benefits of liposomal bupivacaine have not been studied in bariatric patients before and not currently routinely used in bariatric surgery.

Liposomal bupivacaine is distributed in a 20 ml single use vial of 13.3 mg/ml of bupivacaine. The Bupivacaine is encapsulated by liposomes and is slowly released from tissues up to 96 hours after injection. Conventional bupivacaine when injected, has a 3.5-hour half-life. When liposomal bupivacaine is combined with bupivacaine, short acting and long acting pain analgesia is provided. Standard post-operative pain control includes patient controlled analgesia and oral narcotics and oral narcotics for discharge. Inadequate pain control has been shown to prolonged recovery, increased narcotic use, and longer hospital stays [10].

#### Purpose of study:

The purpose of this study is to test the efficacy of liposomal bupivacaine injections compared to standard bupivacaine local surgical site injection in reducing total IV and oral morphine equivalents required after laparoscopic bariatric surgery. With better pain control, we expect a better recovery, with less narcotic requirements, decreasing hospital length of stay and readmission rates and ultimately patient satisfaction from surgery. Use of liposomal bupivacaine is not standard in bariatric laparoscopic surgeries and can change practice to discontinuing PCA use and decrease or eliminate use of narcotics postoperatively.

#### **Design of Study:**

Prospective, double blind- randomized controlled clinical trial.

#### Sample Size:

Approximately 200 patients (100 patients in each arm) are expected to participate in the study. These patients are those that have fulfilled NIH criteria and met preoperative requirements for bariatric surgery. Surgeries and hospital care will be at Fresno Heart and Surgical Hospital (FHSH). Post-operative visits will be at Advanced Laparoscopic Surgical Associates (ALSA).

Methodology used to determine sample size: Utilizing existing data, an estimate was made as to the magnitude of benefit that could be expected for the parameters of interest. Using these estimates, a power analysis was performed to determine the number of patients that would need to be present in each arm for a statistically significant difference at 95% confidence level. Next the estimate of the benefit was reduced to come with the actual number of patients for the study.

#### Patient Population: Exclusion and Inclusion Criteria

#### Gender of subjects:

Population breakdown is expected to be similar to that seen in the adult population seeking bariatric surgery.

Age of subjects:

Adults > 18 years and <65 years.

#### Racial and ethnic origin:

Population breakdown is expected to be similar to that seen in the adult population seeking bariatric surgery. Patients not able to understand or read English will be excluded.

#### Inclusion criteria:

All patients undergoing elective laparoscopic sleeve gastrectomy or Roux-en-Y gastric bypass surgeries.

#### **Exclusion criteria:**

- Patients deemed not a candidate for laparoscopic bariatric surgery
- Patients with previous bariatric or gastric surgeries.
- BMI <35 and > 60 kg/m2
- Preoperative inability to ambulate and confined to wheelchair.
- American Society of Anesthesiologist (ASA) score >3
- Not able to understand informed consent, or unwilling to sign consent.
- Not able to understand and read English
- · Currently pregnant or lactating.
- Age <18 or >65
- Patients intolerant of opiates, NSAIDS, acetaminophen or local anesthetics.
- Patients requiring opiate use within 30 days prior to time of surgery.
- Patients with reported use of narcotics greater than 2 weeks in preceding year before surgery.
- Patients with history of substance abuse, alcohol addiction
- Patients with diagnosis of chronic pain, history of fibromyalgia, chronic regional pain syndrome (dystrophic pain syndrome).
- · Bupivacaine use within 96 hours before operation
- Prisoners
- Patients with renal failure or hepatic failure.
- Intraoperative Exclusion criteria:
- Bariatric surgery operation >3 hours.
- More than 5 laparoscopic incision sites used during surgery, conversion to open operation, placement of a feeding tube or drain.
- Concurrent ventral hernia repair, large hiatal hernia repair or intraoperative extensive lysis of adhesions
- Concurrent cholecystectomy, subtotal gastrectomy, or fundoplication

#### **Randomization:**

If the patient chooses to participate, they will be randomized to 2 arms of either liposomal bupivacaine also known as Exparel® group, or bupivacaine only group on the day of surgery before anesthesia induction in the operating room.

The randomization will be in a 1:1 ratio. The patient and operating surgeon will not be notified which arm the patient is in. The randomization will be done by choosing an envelope in a stack that is previously randomized in a 1:1 ratio by computer program generator. The card in the envelope will state the assigned treatment arm. This will be relayed only to the operating room surgical tech. The randomized card will have an attached patient label and be placed into a locked container for later retrieval by study coordinator and entered into database by end of the operating day. The study coordinator will have access to decode each patient in the study for medical necessity.

The operating room surgical techs and nurses will then prepare the medications and cover the syringes containing the medications with colored sterile tape. Surgical techs and nurses responsible for preparing the medications will verify the medications and doses with one another before covering the syringe with sterile tape. This will impede the surgeon from guessing medication type as liposomal bupivacaine is slightly opaque. All syringes and containers containing study medications will be labeled appropriately with either 1.3% bupivacaine and/or 0.25% bupivacaine and normal saline. The Surgical techs and nurses will announce the medications as "study medications" when delivered to the surgeon and during "Time-Out" procedures. This is in compliance

with CMC Operating Room Policy and Procedure Number 11142.

Once medications are mixed and placed into masked syringes, the surgeon may enter the operating room. At the beginning of the surgery, the patient will be administered local surgical site injections of the assigned medications.

A total of 100 milliliters (mL) mixture of either liposomal bupivacaine (Exparel®) mixed with bupivacaine and saline or bupivacaine mixed with saline will be injected into the surgical incision site at the beginning of surgery. Each surgical site will receive 20 ml of the medication mixture. If in the treatment arm, they will receive 20mL of liposomal bupivacaine diluted with 60 ml of 0.25% Marcaine and 20 ml of saline for a total of 100 ml. If in the bupivacaine only (control) arm, they will receive 60 ml of 0.25% bupivacaine diluted with 40 ml of saline for a total of 100 ml. Dosing is within safety parameters as confirmed with FHSH pharmacy (See attached letter). Additional intraoperative exclusion criteria is outlined above and study coordinator will track patients based on EMR data.

As part of routine post-operative care, the patient will be taken to the recovery unit (PACU) after the operation. The recovery room staff and nursing floor staff, and remaining clinical team not present during randomization in the operating room will be blinded to the type of local anesthetic given. The clinical team including residents, fellows, and remaining surgeons including sub investigator will primarily manage the patient's post-operative care including pain and nausea medications under standard routine ERAS protocol. Management of additional pain and nausea medications will be routinely determined by the non-operating surgeon (other sub-investigators). All patients in the study will receive a standard CMC patient identification wristband and Exparel wristband with warning printed that they should not receive additional bupivacaine for 96 hours after the operation. A study contact number will be added to Exparel wristband for non-Fresno Heart clinicians to call if additional pain medications are to be administered. Per CMC guidelines, Exparel wristbands are not required to be placed as a medical precaution. They have routinely been placed to aid in identifying patients who have received Exparel to aid in ERAS protocols. If patients require return to the operating room within 96 hours after the operation, then liposomal bupivacaine without additional bupivacaine will be administered and study coordinator will be notified of the event.

After discharge, patients will receive a questionnaire to rate daily pain score, daily nausea score, and number of narcotics taken each day. At the first post-operative visit (generally around post-operative day 7), they will be seen by a clinical investigator to review medications, questionnaires, and if any complications relating to surgery or medications administered. Questionnaires and patient journals pertaining to the study will only be limited up until the first post-operative visit.

Patients will be followed as part of standard post-operative bariatric surgery protocol where visits in the office will occur one week post operatively, three weeks post operatively, then routinely every 3-4 months afterwards routinely or more often depending patient routine needs after bariatric surgery. Routinely, patients are then

seen annually in the office as part of their routine health care. There are no additional follow up requirements because patients were involved in the study.

Data will then be analyzed to determine if liposomal bupivacaine has decreased number of total morphine equivalents and has a beneficial effect on surgical care, post-operative nausea, hospital length of stay and readmissions.

## Data Collection:

Patient demographics, medical history, medications, use of narcotic pain medication within 30 days of surgery, hospital course and post-operative course including narcotics, antiemetic use, complications relating to bariatric surgery, follow up compliance, and weight loss after surgery.

- 1. Daily assessments while in hospital:
  - a. Analog pain score (rating scale from 0 to 10 with 0 being no pain and 10 being the worst possible pain on numeric pain intensity scale
  - b. Total IV and oral morphine equivalents administered including use of patient controlled analgesia and breakthrough narcotics.
  - c. Presence of nausea and antiemetic medications administered.
- 2. Hospital course:
  - a. Length of stay, complications requiring interventions or reoperations relating to bariatric surgery, readmission.
- 3. Immediate post-discharge follow-up:
  - a. Analog pain score (rating scale from 0 to 10 with 0 being no pain and 10 being the worst possible pain on numeric pain intensity scale with patient documenting daily pain scores.
  - b. Daily documentation of number of prescription narcotics taken.
  - c. First post-operative visit questionnaire review of pain score, nausea score, and daily requirement of narcotics.
  - d. Assessment of operative complications.

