## **Statistical Analysis**:

Descriptive statistics will be performed on all patients and the demographic data will be examined and compared. Poisson Regression, student's t-test, and non-parametric testing will be used for the analysis of continuous variables. Chi-square analysis will be used for categorical data.

This interventional study is designed to test the null hypothesis that the rate of morphine equivalent units utilized by patients who were administered liposomal bupivacaine (Exparel®) during a primary bariatric surgery is greater than or equal to the rate of patients who were administered Marcaine, versus the alternative hypothesis that the rate of morphine equivalent units utilized by liposomal bupivacaine (Exparel®) during patients is lower than that of bupivacaine only patients. Testing of this hypothesis will be performed for the time period of the inpatient stay, as well as for the period of 7-10 postoperative days.

The sample size selected for this study was chosen to allow for a power of 0.90, an alpha of 0.05, and the ability to detect a rate change of as low as 10% or a 11 unit difference in average daily morphine equivalent units utilized. NCSS/PASS was the statistical software package used for the sample size calculations.

A combination of NCSS and RStudio will be used for the statistical analysis of this study.

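### The morphine-equivalent test over 7-10 postoperative days rests on a home diary count, with no drug, strength or conversion rule specified

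*Combined protocol and SAP*

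**What the plan says.** The Statistical Analysis section states its hypothesis as a rate of morphine equivalent units and adds: "Testing of this hypothesis will be performed for the time period of the inpatient stay, as well as for the period of 7-10 postoperative days". That same section gives the effect the trial is sized for as a 10% rate change or 11 units in average daily use.

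The Data Collection section describes opioid use differently before and after discharge:

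- In hospital (item 1b): "Total IV and oral morphine equivalents administered including use of patient controlled analgesia and breakthrough narcotics".
- At home (item 3b): "Daily documentation of number of prescription narcotics taken".
- At the first visit (item 3c): "First post-operative visit questionnaire review of pain score, nausea score, and daily requirement of narcotics", with no unit given.

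The follow-up text under Randomization describes the home questionnaire in the same way as item 3b: "daily pain score, daily nausea score, and number of narcotics taken each day". It places the first visit at about day 7 and ends the diary there.

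The Hypothesis section is narrower than the Statistical Analysis section. It concerns in-hospital use only.

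**The concern.** The plan tests one quantity in two periods but specifies the matching measurement for only one of them. A number of tablets is not a dose. Converting it needs the product, its strength and a conversion factor, and the plan does not say where these come from for the days at home.

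At stake is one of the two periods in which the hypothesis is tested. Suppose patients in more pain move to a stronger product rather than to more tablets. The arm with worse pain could then show a similar count and a higher dose, and a real benefit would be understated. The opposite error is also possible if the stronger product is more common in the treatment arm. The product taken on each day cannot be reliably rebuilt later if it was not written down at the time.

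**Working it through.** **The plan's own figures.** If the 10% and the 11 units describe the same effect, the control rate is 11 / 0.10 = 110 units per day, the treatment rate is 110 - 11 = 99, and the ratio is 99 / 110 = 0.90. The plan does not say that this effect also applies to the home period. I use it only as a yardstick.

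**Step 1. From count to dose.** For one patient-day, dose = sum over products of (units taken x morphine equivalents per unit). The specified diary gives the total number of units. It specifies neither the split by product nor the equivalents per unit.

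**Step 2. Everyone on one product of one strength.** Let k be the equivalents per unit and N the mean count.

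- Ratio of arms: (k x N_treatment) / (k x N_control) = N_treatment / N_control. The factor cancels, so a 10% contrast could be tested on counts.
- Difference between arms: k x (N_control - N_treatment). The factor does not cancel. For assumed k of 5, 7.5, 10 and 15, a difference of 11 units is 11 / k = 2.2, 1.5, 1.1 and 0.7 tablets per day.

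**Step 3. One product per patient, differing between patients.** The count alone no longer ranks patients by dose. Count times that patient's prescribed strength does, provided the prescription is linked to the diary.

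**Step 4. Several products or a changed prescription.** A daily total cannot be divided between products, so the dose is not determined even when the prescriptions are known.

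**Step 5. Illustration of size.** Assumptions: two strengths, one double the other; equal counts in both arms; counts analysed without adjustment for strength. With p the share of stronger units, mean dose per unit is proportional to 1 + p. The true dose ratio is (1 + p_treatment) / (1 + p_control), while the count ratio is 1. Setting the true ratio to 0.90 gives p_control = (1 + p_treatment) / 0.90 - 1:

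| Stronger units, treatment | Calculation | Stronger units, control |
|---|---|---|
| 30% | 1.30 / 0.90 - 1 | 44% |
| 40% | 1.40 / 0.90 - 1 | 56% |
| 50% | 1.50 / 0.90 - 1 | 67% |

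A gap of about 14 to 17 percentage points is therefore needed to hide a 10% reduction completely. A smaller gap hides part of it: 40% against 50% gives 1.40 / 1.50 = 0.93. A wider one hides more: 30% against 50% gives 1.30 / 1.50 = 0.87.

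**Step 6. The window.** The diary ends at the first visit, generally around day 7, while the test period runs to 7-10 days. For a patient seen on day 7, a window to day 10 has 10 - 7 = 3 days with no diary.

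**The case against.** A reader might infer that the post-discharge test cannot be computed at all. The documents do not support that. At the first visit, "they will be seen by a clinical investigator to review medications, questionnaires" is planned. Data Collection lists medications and "hospital course and post-operative course including narcotics, antiemetic use". The Confidentiality and Privacy section draws data from the electronic records. These sources can give the prescribed product, and for a one-product patient that is enough for an approximation.

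A reader might also infer that the diary form has no drug or strength field. The form itself is not in the documents. All that can be said is that the protocol does not specify such a field. Reading the variable as a number of different drugs is strained beside item 3c.

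Nor do the documents show that bias will occur. They describe no second home strength and no difference between arms, and they do not say that every unit will be counted as one fixed dose. Post-operative pain is managed under a standard protocol by clinicians who are not told the arm. That limits differences caused by knowledge of the arm, but not differences caused by pain itself, which is what the treatment is meant to change.

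Finally, the 7-10 days may simply mean up to the first visit, whenever it falls. The text does not say so.

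What remains is that no section links prescriptions to diary counts, fixes a single discharge product, or states a conversion. The record routes also do not resolve patients with several or changed products.

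**Conclusion.** The gap is real but limited. The hypothesis for 7-10 postoperative days is in morphine equivalents, while the only home opioid variable specified is a daily count with no drug, strength or conversion rule. Dose can be approximated from prescription records for patients on one product throughout, and cannot be for the others. How many patients fall in each group is not stated.

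The size of any bias is unknown. The figure of 40% against about 56% is an illustration that rests on an assumed twofold strength difference, exactly equal counts and no adjustment for strength.

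The in-hospital hypothesis is unaffected, because item 1b measures it directly in morphine equivalents. No length of stay is given, so the share of the 7-10 days spent at home cannot be stated either. This is a low-cost improvement to one of the two test periods and does not put the main hypothesis in doubt.

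**What to change.** - In the follow-up text under Randomization and in Data Collection items 3b and 3c, replace the count with three entries per day: opioid name, strength and number of units taken.
- Pre-print the prescribed product on the diary at discharge and confirm it at the first visit.
- State one morphine-equivalent conversion table in the Statistical Analysis section and use it for both hospital and home doses. The documents contain none at present, so the hospital variable needs it too.
- Align the home analysis window with the end of the diary, so that the test does not extend past the last recorded day.

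The cost is a redesigned diary line, slightly more burden for patients and a few more data-entry fields. It needs no new visit and changes no treatment.
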